
These preclinical studies suggest PNPLA3 as a new therapeutic target, especially with regard to the possibility of reducing its expression in the mutated variant. Therefore, screening based on the determination of the I148M variant status of PNPLA3 could be fundamental for designing future precision medicine approaches. Although the I148M variant of PNPLA3 causes progression of liver damage to advanced fibrosis and hepatocellular carcinoma (1), the phenotypic expression is highly variable and depends on the coexistence of other genetic factors and environmental factors. Furthermore, the relative contribution of the I148M variant carrier state on the steatohepatitis phenotype in

hepatocytes vs. stellate cells is not yet clear. The study of new molecular pharmacological approaches that aim at regulating the expression and activity of PNPLA3 for the prevention and treatment of liver diseases is however still difficult, due to both the limitations of experimental models in animals (cost, suffering, different regulation of lipid metabolism and PNPLA3 compared to humans) and the difficulty of reproducing NASH in models *in vitro*.

The current models *in vitro*, based on liver cell lines, are in fact unable to reproduce the intrinsic cellular heterogeneity, the three-dimensional architecture of the tissue and the cell-cell interactions. These characteristics are fundamental in the study of the processes that can lead to the onset of steatosis, progressing to a fibrotic, cirrhotic and tumorous state following an external insult.

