## 5. ENDPOINTS

### 5.1 Primary Endpoints

1. Isolation of epithelial cells in order to generate models of the main populations of liver cells in a three-dimensional culture environment, called organoids, and molecular characterization of the generated models. Isolation of stellate cells and their phenotypic and molecular characterization. Generation of assemblyloids that mimic the hepatic tissue architecture and its phenotypic and molecular characterization to study the onset and development of steatohepatitis.
2. Evaluation of the impact of the I148M variant (evaluation of possible combinations both in epithelial cells - hepatocytes and in stellate cells) on the steatohepatitic phenotype in human liver assembloids, with particular reference to:
  - Lipid accumulation in hepatocytes (quantitative and qualitative analysis)
  - Lipotoxicity and expression of inflammatory markers (gene expression)
  - Activation of fibrogenesis (assessment of the activation state of stellate cells, retinol metabolism and extracellular matrix deposition)

Steatohepatitis will be defined in the simultaneous presence of all these alterations in the assemblage.

3. Analysis of variants of the TM6SF2, MBOAT7 and GCKR genes, previously correlated with the development of non-alcoholic steatohepatitis (14).

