### Secondary Endpoints

- Knowledge of the behavioral and morphological differences between physiological and NASH hepatocytes and stellate cells.
  - Detection of new biomarkers predictive of the development and progression of the disease.
- a. - Analysis of epigenetic differences in physiological conditions, onset and progression of NASH.

- Knowledge of the molecular mechanisms underlying cellular-level observations using "omics" scale assessments and CRISPR-Cas9 genetic engineering.
- Analysis of the impact of PNPLA3 silencing on the steatohepatitis phenotype of human liver assembloids, stratified by I148M variant carrier status in epithelial cells vs. stellate cells.

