## 7. STATISTICAL ANALYSIS

### 7.1 Sample size and data analysis

The sample size was estimated in view of achieving the two primary outcomes of the project.

Previously published works (24, 25, 26, 27) have shown that the generation efficiency of liver organoids is approximately 100% starting from surgical resections and 33% from biopsies (24, 25).

Considering these estimates, in order to isolate at least 20 independent organoid cultures of each type of condition of interest in our study, we estimate to recruit at least 30 donors for each genetic variant. The intent is to obtain replicates for the analyses with a sufficient representation of the different stages of liver damage (normal liver, inflammation/fibrosis and hepatocellular carcinoma) and to be able to map the impact of the main most common inherited genetic variants (present in at least 20% of individuals) in the population.

For the first primary outcome, the primary analyses will be conducted from single-individual cell cultures. Given the descriptive nature of mapping cellular phenotypes and gene expression, and the large number of organoids ( $>10^3$ ) and cells ( $>10^9$ ) from a single individual, we will have sufficient statistical power (>80%) to identify and analyze specific cellular subsets representing >1% of the overall population.

As regards the second primary outcome, although there are important limitations in the estimate inherent to the type of project and linked to the uncertainty regarding the final characteristics of the model that will be developed during the project, we expect to observe a progressive increase in the

presence and severity of the steatohepatitis phenotype in organoids with increased number of PNPLA3 I148M variants. In particular, we estimated that we could reach a statistical power of 95% (alpha 0.05, two-tailed test) to observe a frequency of steatohepatitis phenotype of 75% vs. 25% in assemblyloids with extreme PNPLA3 genotypes, homozygous for the at-risk variant vs. wild-type (20 cases vs. 20 controls), which is consistent with the increased risk observed in clinical cohorts (28).

Statistical analyses will be performed using JMP (SA, Cary, NC) and R (<https://www.r-project.org>) software and statistical comparisons will be made using the one-way ANOVA or chi-square test, where appropriate. P values < 0.05 will be considered statistically significant.

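### Primary endpoint 2 asks which cell type carries the I148M effect, but section 7.1 names only one-way tests without contrasts, which as written do not attribute it

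*Protocol*

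**What the plan says.** Three places in the Protocol treat the two cell types as separate questions.

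- Section 1.1 gives as an open question "the relative contribution of the I148M variant carrier state on the steatohepatitis phenotype in" hepatocytes as against stellate cells.
- Section 5.1, primary endpoint 2, assesses the impact of I148M on the phenotype through "evaluation of possible combinations both in epithelial cells - hepatocytes and in stellate cells".
- Under Secondary Endpoints, the PNPLA3 silencing analysis is to be "stratified by I148M variant carrier status in epithelial cells vs. stellate cells".

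Section 7.1 gives one sentence on testing for the whole project: "statistical comparisons will be made using the one-way ANOVA or chi-square test, where appropriate". It names no factorial model, interaction, planned contrast or donor term.

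The only power statement for this outcome is single-factor: a "statistical power of 95% (alpha 0.05, two-tailed test") for a "frequency of steatohepatitis phenotype of 75% vs. 25% in assemblyloids with extreme PNPLA3 genotypes", with "20 cases vs. 20 controls". Section 4.1 groups the material by donor genotype alone (CC, CG and GG, 20 patients each). It does not say how many assembloids will be made for each epithelial-by-stellate combination.

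**The concern.** The question has two factors, epithelial genotype and stellate genotype, and the only ANOVA named has one. Over the combinations, a one-way ANOVA or a chi-square test produces a single omnibus p-value. A significant result says that at least one combination differs. It gives no epithelial effect, no stellate effect and no interaction, so the question in section 1.1 stays open even if the endpoint is formally positive. The silencing analysis is exposed in the same way, because it is stratified by the same two factors.

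The method is stated in section 7.1, not deferred. An analysis plan that used a two-factor model would have to go beyond what the Protocol names.

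**Working it through.** **1. The plan's own figure.** Inputs from section 7.1: 75% vs 25%, 20 per group, two-sided alpha 0.05.

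- Unpooled normal approximation: SE = √(2 × 0.1875/20) = 0.1369; 0.5/0.1369 − 1.96 = 1.69; power 95.5%. This reproduces the stated 95%.
- Pooled variance under the null, which corresponds to the uncorrected chi-square test: (0.5 − 1.96 × √(2 × 0.25/20))/0.1369 = 1.39; power 91.7%.

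Both concern one binary comparison of extreme genotypes. Neither involves the combinations, so the figure does not bear on this point and the fix does not change it.

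**2. What each analysis estimates.** Take four combinations (wild-type or homozygous 148M in each cell type) with means μ00, μ01, μ10, μ11, epithelium first.

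| Quantity | Expression | In the omnibus test? |
|---|---|---|
| Any difference | all four means equal (3 df) | yes |
| Epithelial effect | (μ10 + μ11 − μ00 − μ01)/2 | not separately |
| Stellate effect | (μ01 + μ11 − μ00 − μ10)/2 | not separately |
| Interaction | μ00 − μ01 − μ10 + μ11 | not separately |

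The last three are single-df contrasts in the same four means. In a simulated balanced data set, contrasts in the one-way cell-means model gave the same F values as the two-way model: 8.62, 9.29 and 0.54. So one-way ANOVA with these contrasts would answer the question, but section 7.1 names none.

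**3. Power, for illustration.** The documents give no SD, no effect per cell type and no number per combination. Assumed: balanced 2x2, m independent assembloids per combination, N = 4m, SD 1, no interaction, alpha 0.05.

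Noncentrality: λE = N·dE²/4 for the epithelial main effect, on F(1, N−4); λ = N(dE² + dS²)/4 for the omnibus test, on F(3, N−4).

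For m = 10 and dE = 0.8: λE = 40 × 0.64/4 = 6.4. The omnibus λ is 6.4 if dS = 0 and 12.8 if dS = 0.8.

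| m | dE | dS | Omnibus | Epithelial main effect |
|---|---|---|---|---|
| 10 | 0.8 | 0 | 50% | 69% |
| 10 | 0.8 | 0.8 | 82% | 69% |
| 10 | 1.0 | 0 | 71% | 87% |
| 10 | 1.0 | 1.0 | 96% | 87% |
| 20 | 0.8 | 0 | 85% | 94% |
| 20 | 0.8 | 0.8 | 99% | 94% |

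The omnibus test is weaker when one cell type acts and stronger when both do. In neither case does it say which.

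For a 3x3 layout, assume 6 per combination and 0.5 SD per epithelial allele only, so λ = 18 × 2 × 0.25 = 9. Power is 46% for the omnibus test on F(8, 45), 74% for a 2-df epithelial factor and 84% for a 1-df allele trend. The step from 74% to 84% comes from assuming linearity, not from using two factors.

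**4. Coding of the replacement model.** With uncentred counts and their product, the epithelial coefficient is the effect at zero stellate risk alleles. In the 2x2 with 1 SD, its λ is m·dE²/2 = 5 and its power 59%. In the 3x3 it is 46%. Centring restores the main effect (87% and 84%).

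**5. Identifiability.** If both cell types come from one donor, the two genotypes are equal. The design matrix (intercept, epithelial count, stellate count) then has rank 2 for 3 parameters, and no test separates the effects. Assembloids that cross donors of different genotype are required.

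**The case against.** The strongest reply is that a one-way ANOVA is not barred from separating the cell types. With planned contrasts it is algebraically the two-way model, and section 7.1 does not say that analysis stops at the omnibus test. The sentence is a summary for the whole project, qualified by a clause on appropriateness, and contrasts are often left to an analysis plan. Part of this stands: a reader might infer that the named test can never answer the question, and that would be wrong. What remains is that the Protocol fixes a one-factor method for a two-factor primary question and names nothing that would attribute the effect. The qualifying clause chooses between the two tests listed and adds no third.

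A reader might also infer that the one-way test always wastes power, or that the stated 95% is too high for this reason. The documents support neither. The losses appear only where one cell type acts alone, under assumed sizes and effects. Section 2 hypothesises loss of function in both cell types, and there the omnibus test has the higher power. The 95% belongs to a different, binary comparison.

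Finally, changing the test alone is not enough. Section 4.1 groups by donor genotype only, and same-donor assembloids cannot separate the effects under any model. This objection stands in full and shapes the fix.

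**Conclusion.** The point holds as a mismatch between a primary endpoint and its named test. As written, an omnibus one-way ANOVA or chi-square over the combinations does not say which cell type carries the I148M effect, although sections 1.1 and 5.1 and the silencing endpoint all ask for that. This conclusion rests on the text alone and needs no assumed numbers.

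The effect on power is secondary and its direction depends on the truth. Under the assumed 2x2 with 10 per combination and 0.8 SD, the omnibus test is 19 points below the epithelial main effect if only epithelium acts (50% vs 69%) and 13 points above it if both act (82% vs 69%). These figures assume independent assembloids, balance and no interaction. The change is worth making but does not threaten the validity of the study.

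**What to change.** In section 7.1, for primary endpoint 2, replace the one-way test with wording such as:

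> Assembloids combining epithelial and stellate cells from donors of different PNPLA3 genotype will be analysed with a two-factor model. The terms are epithelial I148M genotype and stellate I148M genotype, entered as centred allele counts or effect-coded factors, and their interaction. The model is linear for graded readings and logistic for the composite phenotype, with a donor random effect where donor lines are reused. Both main effects and the interaction will be reported with 95% confidence intervals, and cell-type-specific simple effects if interaction is present.

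State why crossing is needed: same-donor assembloids cannot separate the two effects. Give the intended number of assembloids per combination. Use the same two factors for the silencing analysis under Secondary Endpoints.

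The cost is a few sentences and somewhat more analysis work; R, already named in section 7.1, can fit these models. The crossed assembloids that endpoint 2 already implies must be made from the planned donor lines, which is laboratory work. The model itself calls for no additional donors, but whether the number per combination is adequate cannot be judged until it is stated.

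### The single P < 0.05 rule in section 7.1 has no exception for the omics, epigenetic, non-coding RNA and biomarker screens; these need a false-discovery-rate rule

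*Protocol*

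**What the plan says.** Section 7.1 names the software and the tests: "statistical comparisons will be made using the one-way ANOVA or chi-square test, where appropriate". The next sentence gives the threshold: "P values < 0.05 will be considered statistically significant". It names no tier, family of tests or exception.

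The same section powers one comparison, homozygous risk-variant against wild-type assembloids with 20 in each group ("alpha 0.05, two-tailed test"). The anticipated difference is a "frequency of steatohepatitis phenotype of 75% vs. 25" per cent.

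Other sections plan analyses of a different kind:
- Secondary Endpoints (section 5) lists molecular work using omics "scale assessments and CRISPR-Cas9 genetic engineering", a comparison of epigenetic differences across disease stages, and "Detection of new biomarkers predictive of the development and progression of the disease".
- Section 2.2 makes new non-invasive biomarkers a secondary objective, to be validated later in clinical series.
- Section 3.2 requires blood for epigenetic analysis and for three classes of non-coding RNA (lncRNA, miRNA, circRNA).

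None of these sections gives a threshold or says how many features will be tested.

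**The concern.** A 0.05 threshold suits one planned comparison. In a screen it fixes the proportion of null features declared significant, not the proportion of declared findings that are false. When many features are tested and few truly differ, the second proportion can be high even if every test is done correctly.

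The candidate list is a stated product of this study, since biomarkers are to go forward to clinical series. A list with a high false share uses up validation samples on leads that will fail. The epigenetic and omics results would also be reported as significant under a rule that does not control their error.

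**Working it through.** **1. The protocol's own figure.** Inputs from section 7.1: 75% vs 25%, 20 per group, two-sided 0.05, stated power 95%.
- Unpooled normal approximation: SE = √(2 × 0.75 × 0.25 / 20) = 0.137. Power = Φ(0.5/0.137 − 1.96) = Φ(1.69) = 95.5%. This reproduces the stated figure.
- Pooled variance under the null: SE₀ = √(2 × 0.5 × 0.5 / 20) = 0.158. Power = Φ((0.5 − 1.96 × 0.158)/0.137) = Φ(1.39) = 91.7%. The exact power of the uncorrected chi-square test is 90.1%.

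Power is above 90% by each of these methods, and this is one test at 0.05. The threshold is sound for this comparison.

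**2. False positives in a screen.** The expected number is 0.05 × the number of null features. The counts below are assumptions.

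| Null features | Expected declared significant |
|---|---|
| 100 | 5 |
| 1,000 | 50 |
| 20,000 | 1,000 |

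**3. False share of declared discoveries.** Let π be the share of features that truly differ (assumed). Then false share = 0.05(1 − π) / [0.05(1 − π) + power × π].

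At 80% power:
- π = 1%: 0.0495 / (0.0495 + 0.008) = 86%
- π = 5%: 0.0475 / (0.0475 + 0.040) = 54%
- π = 10%: 0.045 / (0.045 + 0.080) = 36%
- π = 20%: 0.040 / (0.040 + 0.160) = 20%

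At 50% power the same four values are 91%, 66%, 47% and 29%.

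**4. When more than half are false.** Setting the false share to one half gives π = 0.05 / (0.05 + power). That is 5.9% at 80% power, 9.1% at 50% and 20% at 20%.

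**5. Is 80% power reasonable here?** With 20 vs 20 and a normal approximation, power at 0.05 is Φ(d√10 − 1.96) for a standardised difference d. This gives 35% at d = 0.5, 72% at d = 0.8 and 89% at d = 1. So 80% power needs a difference of between 0.8 and 1 SD. Smaller effects mean lower power and a higher false share.

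**The case against.** The best defence is that the threshold sentence does not mention omics, epigenetics or biomarkers, and does not say that P values are unadjusted. A 0.05 cut-off on adjusted P values would be compatible with it. Multiplicity in secondary screens is often left to a statistical analysis plan, and one may exist. The secondary endpoints are worded as knowledge and detection, and biomarkers must still pass later validation.

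Part of this stands. That the screens are covered is inferred from unqualified wording and from the absence of any other rule. Later validation limits the harm for biomarkers. But the protocol is not simply silent: it states a threshold without exception, directly after naming the tests. An analysis plan using a false-discovery-rate rule would have to qualify that text. Later validation sets no threshold for the screen itself.

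A reader might infer more than the protocol supports, in three ways:
- **That the steatohepatitis endpoint has no error control.** Section 5.1 requires all the alterations to be present together, so the three domains form one phenotype, and section 7.1 powers one test of it at 0.05. The protocol does not lay out separate domain tests, and a Holm correction for them would be a matter of preference.
- **That four genes crossed with three domains make 12 tests, with a 46% family-wise error (1 − 0.95¹²).** Section 5.1 says only "Analysis of variants of the TM6SF2, MBOAT7 and GCKR genes" and crosses them with nothing.
- **That the nine fibrogenic and retinol genes named in section 4.8 carry a 37% family-wise error (1 − 0.95⁹).** That figure needs independence. These genes are joint markers of stellate-cell activation and retinol metabolism, so correlation is likely.

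**Conclusion.** The point holds for the screens only. The protocol states one threshold, without exception or adjustment, and its own screening endpoints need a different one.

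The rate of about 5% of null features follows directly from the rule; 1,000 false positives depends on an assumed 20,000 null features. The false shares depend on assumed power and on an assumed proportion of true effects, neither of which the protocol gives. It would therefore be too strong to say that the screens will yield mainly noise. At 80% power that is true only when fewer than about 6% of features differ; at 10% the false share is 36%. The boundary moves up to about 9% at 50% power. The composite comparison needs no change.

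**What to change.** Change the last sentence of section 7.1 in two parts:
1. Limit the two-sided 0.05 rule to the composite steatohepatitis phenotype by PNPLA3 genotype.
2. State that the omics, epigenetic, non-coding RNA and biomarker screens will each be judged by Benjamini-Hochberg false discovery rate at 5%, within that screen.

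Say expressly that the TM6SF2, MBOAT7 and GCKR analysis remains a primary endpoint. A blanket statement that all other P values are exploratory would demote it without saying so.

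The cost is protocol wording, carried into any analysis plan. No donors, samples or assays are added, and the power of the composite comparison is unchanged. The downside is fewer nominal hits. For a 1 SD difference at 20 vs 20, power per feature is 89% at 0.05. It would be 6% under a full Bonferroni correction for 20,000 features (0.05/20,000, normal approximation). Benjamini-Hochberg lies between the two, which is why it suits discovery better than family-wise control.

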## 8. ADVERSE EVENTS

The project does not involve the administration of drugs or other substances or ad hoc invasive interventions outside of normal clinical practices. Therefore, no adverse events are expected.

## 9. RISK/BENEFIT ASSESSMENT

The study does not foresee an immediate benefit for patients, but the results of this trial will have the potential to lead to a decoding of the mechanisms underlying the development of NASH, resolve the temporal order of events that regulate its evolutionary trajectory, understand its progression, characterization and improve the therapeutic management of patients.

## 10. STUDIO MANAGEMENT

### 10.1 Data collection and management

Each participant will be assigned a unique code at enrollment. The file that associates the participant code with the participant identification data will be stored separately on a password-protected computer. The study database will be password-protected and uploaded to a password-protected computer and accessible only to study personnel designated by the principal investigator. De-identification of the data will be done in such a way that researchers accessing the database will not be able to trace the identity of the subjects in any way. Only local investigators will be able to trace the identity of the enrolled subjects.

### 10.2 Regulatory aspects and ethical considerations

### 10.2.1 Approval by the Competent Authority

In accordance with applicable regulations, the principal investigator must obtain approval from the appropriate Competent Authority prior to initiating the clinical study.

This study will be conducted in accordance with the ICH/GCP (International Conference of Harmonization/Good Clinical Practice) and all applicable laws, including the Helsinki Declaration of June 1964, as amended by the last World Medical Association General Assembly in Seoul, 2008.

### 10.2.2 Ethics Committee Approval

The investigator must ensure that the protocol has been reviewed and approved by the local independent Ethics Committee (EC) before starting the study.

The CE must also review and approve the informed consent (IC) form and all written information received from the patient prior to enrollment in the study.

If it is necessary to modify the protocol and/or the IC during the study, the investigator will be the guarantor and therefore the person responsible for ensuring the review and approval of such modified document as requested by the CE.

The content of these changes will be implemented only after the CE has approved them. Until then, it will be necessary to refer to the previous version of the document already approved.

